## 5.2. Masking

This is a subject-masked study. Masking will be used to reduce potential bias. Subjects will be unaware of the identity of the investigational product. Investigators and clinical site personnel involved in the data collection will not be masked as to the identity of the investigational product. Although the subjects will not be aware of which study lens is going on which eye, the dynamic nature of the test lens during the assessments may give the identity.

Under normal circumstances, the mask should not be broken until all subjects have completed the study and the database is finalized. Otherwise, the mask should be broken only if specific emergency treatment/course of action would be dictated by knowing the treatment status of the subject. In such cases, the Investigator may, in an emergency, contact the medical monitor. In the event the mask is broken, the Sponsor must be informed as soon as possible. The date, time, and reason for the unmasking must be documented in the subject record. The Investigator is also advised not to reveal the study treatment assignment to the clinical site or Sponsor personnel.

Subjects who have had their treatment assignment unmasked are expected to return for all remaining scheduled evaluations. Subjects who are discontinued will be replaced.

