#### Investigational contact lenses

The investigational lenses will be tested with an additional UV/HEV light source as one of the test conditions. "Activation" will be achieved using an ultraviolet activator consisting of LEDs waveband 365-400 nm that combines with the primary optical path of the system, after the final lens of the optical system (see Figure 7). The spectral output of the ultraviolet LEDs is given in Appendix G. The ultra-violet LEDs will be used, at a low constant rate, while the visual measures (halos, etc.) are being collected. The overall energy at the plane of the eye is 64  $\mu$ w/cm2 (measured using the ILT 950, the graph in Appendix G is the light source at the energy we plan to use during the measurement). As a comparison, the UV activator emits 0.07 mw/cm2 whereas mid-day sunlight measured 11 mw/cm2 using the same instrument (1:00 PM, partially cloudy day, September 18, 2017, Athens, GA using a UVA light meter: General UV254SD).

JJVC CONFIDENTIAL

JJVC CONFIDENTIAL

	Psychometric Testing B: Dysphotopsia Evaluation			
	The psychophysical tests described in Steps 1-3 below may occur in any order. All three tests will perfomed twice: once with an UV/HEV activating light source and once with no activating light source. The order of light source testing will be randomized.			
Step	Procedure	Details		
1	Two-point Light Spread Function	These thresholds are defined as the minimum distance that two points of light are completely distinct. An ascending and a descending method of limits will be used. This measurement takes about 10-15 minutes. Record values OD and OS, in mm (2 decimal places).		
2	Starburst	This is defined as the diameter of the light's lateral spread. Subjects will have the nature of starbursts explained using visual aids prior to the experiment. The investigator will adjust a calibrated custom-made micrometer (two sides with reverse threading) to spread two posts out from a central mid-point. Those posts will be used to define the outer boundaries of the starburst image. Ascending and descending methods of limits would be used based on subject feedback. This measurement takes about 10-15		

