## 14.2. Sample Size Justification

The plan is to enroll a maximum of 66 subjects with a minimum target of 60 subjects to complete. The sample size was chosen by the study responsible clinician and was not based on any empirical power calculation. Furthermore, a power calculation cannot be provided for any of the primary endpoints because no historical data is available. This data from this study will be utilized in the sample size calculations for any additional follow-up studies.

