## 14.4. Level of Statistical Significance

Each primary and secondary hypothesis will be tested individually using a type I error rate of 5%.

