# 14.5. Primary Analysis

# Light Scattering (Two-point Light Spread Function)

This is defined as the minimum distance (mm) that two points of light are completely distinct. This threshold will be analyzed by a linear mixed model. Sequence of lens wear, lens type, age group, dominant eye and the interaction between lens type and age group will be included in the model as fixed effects. An appropriate covariance structure will be used to model the residual errors between measurements between eyes within a subject. The variance-covariance structure will be selected based on the finite-sample corrected Akaike's Information Criterion Corrected (AICC). The structure that returns the lowest AICC will be deemed the most appropriate structure. Covariance structures under consideration include:

- Unstructured (UN)
- Compound Symmetry (CS)
- Heterogeneous Compound Symmetry (CSH)

Heterogeneous covariance structures across lens type may be considered if necessary. The Kenward and Roger method (Kenward and Roger, 1997) will be used for the denominator degrees of freedom.

Comparisons between lenses (Test inactivated vs Control and Test activated vs Control) will be carried out using 2-sided 95% confidence intervals constructed for the least-square mean (LSM) difference (Test – Control). Statistically significantly lower differences of the Test lens relative to the Control lens will be concluded if the upper limit of the 95% confidence interval is below 0. If the interaction between lens type and age is significant then comparisons between lenses will be made within age group.

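### Which eye is tested first is neither fixed, randomised nor recorded, and the models carry no right/left-eye or eye-order term: a possible bias if order tracks lens, and needlessly wide intervals if it does not

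*Combined protocol and SAP*

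**What the plan says.** Section 5.1 randomises, at Visit 2, which eye wears the Test lens (blocks of two) and the order of the activated and inactivated rounds. Section 7.2, Psychometric Testing B, asks for the two-point, starburst and halo readings with the instruction "Record values OD and OS, in mm (2 decimal places". Its one sentence on free ordering, "The psychophysical tests described in Steps 1-3 below may occur in any order", is about the three tests, not the eyes. No text fixes, randomises or asks to record which eye goes first, in Testing B or in Testing A at Visit 1.

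On masking, section 5.2 states: "Investigators and clinical site personnel involved in the data collection will not be masked as to the identity of the investigational product". For starbursts and halos the investigator moves the micrometer posts in response to the subject.

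The primary model in section 14.5 is listed as follows: "Sequence of lens wear, lens type, age group, dominant eye and the interaction between lens type and age group will be included". Starbursts and halos use the same model, and section 14.6 uses the same terms. Success rests on "2-sided 95% confidence intervals constructed for the least-square mean (LSM) difference" with the upper limit below zero for the primary endpoints. Section 4.2 calls carryover unlikely because of the time between measures. It does not discuss practice or fatigue between the two eyes within a test.

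**The concern.** Each primary test takes 10 to 15 minutes and uses ascending and descending limits, and all three are run in two rounds. At Visit 1, recovery and squint follow a bleaching exposure. A difference between the first and second eye tested is therefore plausible, and the plan does not say how it is kept apart from the lens effect.

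Two things could be at stake. If eye order were associated with lens, the order effect would enter Test minus Control directly. If order is unrelated to lens, the estimate is unbiased but the effect stays in the residual. Sequence is a between-subject term and cannot absorb it. The right/left effect is the sequence-by-lens interaction, which the model leaves out. This is like a crossover model with sequence but no period. Section 14.2 says the sample size "was not based on any empirical power calculation", so no documented margin covers lost precision.

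**Working it through.** **Inputs from the documents.** Planned size: "The plan is to enroll a maximum of 66 subjects with a minimum target of 60 subjects to complete" (14.2). Age split: 40 and 20 (4.3). Lens-to-eye allocation: 1:1 in blocks of two (5.1). Each hypothesis is tested at 5% (14.4).

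**Assumptions.** The SD of the between-eye difference is not given, so it is set to 1. The order or right-left effect k is not given either, so 0.25, 0.5 and 1.0 SD are tried. Each lens comparison is treated as one Test-minus-Control difference per subject.

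**The plan's own figures.** The loss implied by 66 and 60 is 6/66 = 9.1%. There is no stated power to reproduce. With no order effect, the half-width for equally weighted age groups is about 2.0 × 0.5 × √(1/40 + 1/20) = 2.0 × 0.137 = 0.27 SD. Simulation (6,000 runs per setting) gives 0.272, with type I error 5.1% against the nominal 5%.

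**Case 1: right eye always first.** D = δ + k·s + ε, with s = +1 or −1 according to which eye has the Test lens, and ε of SD 1. With s balanced, the mean of D is δ, so there is no bias. Without an eye term the residual variance is 1 + k², so the width is multiplied by √(1 + k²) and the effective number of subjects is 60/(1 + k²).

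| k | √(1 + k²) | Effective n | Half-width, no eye term | Half-width, eye term | Coverage, no eye term | Two-sided type I error, no eye term | Power for 0.362 SD, no eye term | Power, eye term |
|---|---|---|---|---|---|---|---|---|
| 0.25 | 1.03 | 56 | 0.281 | 0.273 | 95.5% | 4.5% | 72% | 73% |
| 0.5 | 1.12 | 48 | 0.306 | 0.272 | 97.0% | 3.0% | 66% | 75% |
| 1.0 | 1.41 | 30 | 0.390 | 0.274 | 99.4% | 0.6% | 42% | 74% |

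With k = 0 the power is 73%.

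**Covariance choice.** A small REML check on two records per subject (25 data sets per value of k) gave a mean model SE of 0.138, 0.152 and 0.189 for k = 0, 0.5 and 1.0. The values were identical under compound symmetry and unstructured. With an eye term they were 0.138, 0.135 and 0.132. Neither the sequence term nor the covariance choice removes the effect.

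**Dominant-eye term.** The table leaves it out. Coded per subject, it absorbs nothing from the difference. Coded per eye at k = 0.5, the half-width falls from 0.31 to 0.306, 0.296 or 0.286 if 65%, 80% or 90% of subjects are right-dominant (assumed shares), against 0.27 with an eye term. At 80% that recovers (0.31 − 0.296)/(0.31 − 0.27) = 35% of the loss, and at 90% it recovers 60%. The table is therefore an upper bound.

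**Case 2: first eye random, independent of lens, not modelled.** Coverage stays near 95%, but the width is inflated about as much. At k = 0.5 the half-width is 0.305 both without and with an OD/OS term. A first/second-tested term brings it to 0.276.

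**Case 3: order associated with lens.** If the Test eye is first in a share p of subjects, the lens contrast shifts by (2p − 1)·k. For illustration only, p = 0.75 gives a shift of 0.5k, that is 0.125, 0.25 or 0.50 SD. If first readings run lower, false claims that Test is lower occur in 14%, 39% or 77% of trials, against 2.5% nominal. With the opposite sign, a real benefit is hidden. At p = 1, order and lens are identical and no model term can separate them.

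**The case against.** The strongest reply is that every effect size is assumed. The documents report no order or right-left effect, and section 14.2 says there are no historical data. At 0.25 SD the loss is about 3% in width and one or two points of power. The large figures need an effect as big as a whole SD of the paired difference. The dominant-eye term may take up some of it, and the planned ascending and descending runs offset direction-dependent errors. All of this stands, although paired runs do not remove practice or fatigue between eyes.

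A reader might infer that unmasked testers will order the eyes by lens and tilt the result towards the Test lens. The documents do not support that. They are silent on eye order, no share p can be drawn from them, and the wording "Record values OD and OS, in mm (2 decimal places" suggests right then left if anything. Under that order randomisation removes the bias, and the error rate falls below nominal. The study flowchart (Figure 1) is not shown in the copy reviewed. If it sets eye order, only the model half of the point remains.

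A reader might also take the freedom to run the three tests in any order as part of this problem. It is a separate matter, and the calculation gives no ground for asking that test order be the same in both rounds.

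**Conclusion.** The point holds as a gap in both design and model. Eye order is not set or recorded, the testers know the lens, and the models have no term for right/left eye or tested order. Bias is only conditional: it needs both an order effect and an order associated with lens. Under the more natural right-then-left order the harm is conservative, namely intervals up to about 3%, 12% or 41% too wide at assumed effects of 0.25, 0.5 or 1.0 SD, with balanced lens allocation and 60 completers. These are not estimates of what will happen in this trial, and no stated power figure is contradicted. The change is still worth making before enrolment, because an order that was neither fixed nor recorded cannot be recovered afterwards.

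**What to change.** Choose one of two routes and apply it to both Testing A and Testing B.

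- **Fixed order.** State that the right eye is always tested first in every test and round, and add eye (OD/OS) as a fixed effect to the models in sections 14.5 and 14.6.
- **Randomised order.** Put the first-tested eye on the randomisation list, balanced against lens. Record it, and add a first/second-tested-eye term to the models. An OD/OS term alone does not capture order on this route.

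The first route is simpler. The cost is one sentence per procedure and one degree of freedom, with no added visit time; the second route also needs a column on the randomisation list and one recorded field.

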# FINAL EVALUATION

The final evaluation will ordinarily take place immediately following the last scheduled follow-up visit per the study protocol. It may also take place at any point the subject discontinues the study or is terminated from the study.

Final Evaluation			
Step	Procedure	Details	
F.1	Final Exam Form	Indicate if the subject completed the study successfully. If subject discontinued from the study, indicate the reason.	
F.2	Subjective spherocylindrical Refraction	Perform bare-eye subjective spherocylindrical refraction with a phoropter and record the best corrected distance visual acuity to the nearest letter (OD, OS, and OU).	

## 7.3. Unscheduled Visits

If, during the investigation, a subject requires an unscheduled visit to the clinical site, the following information will be collected at a minimum:

- Chief complaint prompting the visit. If the reason is an adverse event, the applicable eCRF for the adverse event must be completed and subject record completed as appropriate
- Date and time of the visit and all procedures completed at the unscheduled visit
- Review of adverse event and concomitant medications
- Documentation of any test article dispensed or collected from the subject, if applicable
- Slit lamp findings (using the Slit Lamp Classification Scale)

If the Investigator withdraws a subject from the study, the final study visit case report forms must be completed indicating the reason(s) why the subject was withdrawn. The subject record must be completed documenting the date and primary reason for withdrawal and the study CRA notified.

Any ocular and non-ocular Adverse Events that are ongoing at the time of the study visit will be followed by the Investigator, within licensure, until they have resolved, returned to pretreatment status, stabilized, or been satisfactorily explained. If further treatment i.e., beyond licensure is required, the subject will be referred to the appropriate health care provider.

Unscheduled Visit			
Step	Procedure	Details	
U.1	Chief Complaints	Record the subject's chief complaints for reasons for the unscheduled visit.	
U.2	Adverse Events and Concomitant Medications Review	Review any changes to the subject's medical history or concomitant medications from the previous study visit. Record any changes, and any adverse events.	
U.3	Entrance VA	Record the entrance distance visual acuity (OD, OS and OU) to the nearest letter.	
U.4	Subjective Sphero- cylindrical Refraction	Perform bare-eye subjective spherocylindrical refraction with a phoropter (adopt the maximum plus to maximum visual acuity (MPMVA) approach and use the duo-chrome test for binocular balancing) and record the best corrected distance visual acuity to the nearest letter (OD, OS, and OU).	
U.5	Slit Lamp Biomicroscopy	FDA Slit Lamp Classification Scale will be used to grade the findings. If the clearance of the fluorescein needs to be expedited, preservative-free rewetting drops may be instilled.	
U.6	Exit Visual Acuity	Record the subject's exit distance visual acuity (OD, OS, and OU) to the nearest letter.	

The following information will be collected during an unscheduled visit.

## 7.4. Laboratory Procedures

The optical bench will be used to measure the light transmission characteristics for all worn Test lenses. The findings are for internal information only and will not be part of the final report.

# 8. SUBJECTS COMPLETION/WITHDRAWAL

# 8.1. Completion Criteria

Subjects are considered to have completed the study if they have completed all scheduled visits.

# 8.2. Withdrawal/Discontinuation from the Study

A subject will be withdrawn from the study for any of the following reasons:

- Subject death during the study period
- Subject withdrawal of consent
- Subject not compliant to protocol (e.g. Subject more than 2 days out of visit window).
- Subject lost to follow-up
- Subject no longer meets eligibility criteria (e.g. the subject becomes pregnant)
- Subject develops significant or serious adverse events causing discontinuation of study lens wear (subjects missing more than 2 days of missed lens wear within a period 1 of week should be discontinued)
- Subjects who have experienced a Corneal Infiltrative Event (CIE)
- Investigator's clinical judgment regarding the subject safety reasons (that it is in the best interest of the subject to stop treatment)
- Subject missed any scheduled study visits
- Subject not compliant with study lens wear schedule
- Subject not successfully dispensed due to lack of efficacy and safety including poor vision, poor comfort or unacceptable fit

For discontinued subjects, the Investigator will:

- Complete the current visit (scheduled or unscheduled)
- Complete the Final Evaluation, indicating the reason that the subject was discontinued from the study
- Record the spherocylindrical refraction with best corrected distance visual acuity
- Collect used test article(s) (worn or brought to the visit) from the subject and discard them, unless otherwise stated in Section 7.2. Collect all unused test article(s) from the subject.

Investigator will discuss with sponsor before enrolling any additional subjects if a subject discontinues from the study prematurely.

In cases where a subject is lost to follow-up, every possible effort must be made to contact the subject and determine the reason for discontinuation/withdrawal. The measures taken to follow up must be documented including two written attempts and a certified letter (or equivalent) as the final attempt.

# 9. PRE-STUDY AND CONCOMITANT INTERVENTION/MEDICATION

Concomitant medications will be documented during screening and updated during the study. Disallowed medications for this study include: See section 3.3 Concomitant therapies that are disallowed include: See section 3.3

# **10. DEVIATIONS FROM THE PROTOCOL**

Investigator will notify study sponsor upon identification of a protocol deviation. Major protocol deviations must be reported to the sponsor within 24 hours after discovery of the protocol deviation. The Investigator will report deviations per IRB/IEC requirements. All deviations will be tracked and corrective actions implemented as appropriate.

If it becomes necessary for the Investigator to implement a deviation in order to eliminate an immediate hazard to the trial subject, the Investigator may implement the deviation immediately without notification to the sponsor. Within 24 hours after the implemented deviation, the Investigator must notify and provide the rationale to the Sponsor and, as required, the IEC/IRB.

# **11. STUDY TERMINATION**

The occurrence of one or more Unanticipated Serious Adverse Device Effect (USADE), or any SAE where the relationship to study agent cannot be ruled out, may result in stopping further dispensing of test article. In the event of a USADE or SAE, the Sponsor may unmask the treatment regimen for the subject(s) and will discuss this with the Investigator before any further subjects are enrolled.

The Sponsor will determine when a study will be stopped. The Principal Investigator always has the discretion to initiate stopping the study based on patient safety or if information indicates the study's results are compromised.

JJVC reserves the right to terminate the study at any time for any reason. Additionally, the IEC/IRB reserves the right to terminate the study if an unreasonable risk is determined. The study can be terminated by the Principal Investigator at the individual clinical site due to specific clinical observations, if in their opinion, after a discussion with JJVC, it is determined that it would be unwise to continue at the clinical site.

JJVC (and the IEC/IRB and DMC, if applicable) will evaluate all adverse events. If it is determined that an adverse event presents an unreasonable risk, the investigation, or that part of the investigation presenting the risk, will be terminated, as soon as possible.

Should the study be terminated (either prematurely or as scheduled), the Investigator will notify the IEC/IRB and Regulatory Authority as required by local regulatory requirements.

# **12. PROCEDURE FOR HANDLING PRODUCT QUALITY COMPLAINTS**

A Product Quality Complaint (PQC) refers to any written, electronic, or oral communication that alleges deficiencies related to the identity, quality, durability, reliability, safety, effectiveness or performance of test articles after they have been released for clinical trial use.

Potential complaints may come from a variety of sources including but not limited to subjects, clinical research associates (CRA), clinical operations managers (COM), medical monitors, and site personnel, etc. The following are not considered product quality complaints:

- Subject satisfaction inquiries reported via "Subjective Questionnaires" and "Patient Reported Outcomes (PRO)"
- Clinical test articles that are stored improperly or damaged after receipt at the investigational site
- Lens replacements that occur due to drops/fall-outs
- Damage deemed by clinicians or clinical staff to be caused by handling by the user, and not indicative of a quality deficiency (i.e. tears, rips, etc.), only in situations where there is no deficiency alleged by the subject

Within 24 hours of site personnel becoming aware that a PQC has occurred, the PQC must be recorded in the EDC system, which will trigger an automatic email notification to the appropriate COM/CRA and Clinical QA representative. In cases where the EDC system in use is not configured to send automatic notifications or when an EDC system is not used, the COM/CRA is responsible for notifying Clinical QA upon discovery that a PQC has occurred.

Upon receipt of the EDC notification, the COM/CRA will contact the study site to collect additional information which will include:

- Date the complaint was received/recorded in the EDC System (Date of Sponsor Awareness)
- Who received the complaint
- Study number
- Clinical site information (contact name, site ID, telephone number)
- Lot number(s)
- Unique Subject Identifier(s)
- Indication of who first observed complaint (site personnel or subject)
- OD/OS indication, along with whether the lens was inserted
- Any related AE number if applicable
- Detailed complaint description (scheduled/unscheduled visit, wear time, symptoms, resolution of symptoms, etc.)
- Eye Care Provider objective (slit lamp) findings if applicable
- Confirmation of product availability for return (and tracking information, if available), or rationale if product is not available for return

Once a complaint is received, it will be assessed by the COM, CRA, or trained site personnel to determine if it is an Adverse Event/Serious Adverse Event (AE/SAE). If the complaint results in an AE/SAE, the COM/CRA, or trained site personnel will follow Section 13 of this protocol. If the AE/SAE was potentially the result of a product quality related deficiency, these procedures also applies and will be executed in parallel.

In some cases, a PQC form may be generated in EDC by the site in error. In this event, the PQC forms will be marked "Intentionally Left Blank" or "ILB". Justification for ILB must be documented.

JJVC CONFIDENTIAL

